6.6.1. Data Collection

Data will be obtained from direct subject observation, review of the subject's electronic medical record, scheduled and unscheduled follow-up visits (which may be in-person or by telephone), as detailed above. For subjects who withdraw consent to participate in the study, data collected up until the time of withdrawal will be kept, but no further data will be collected.

6.6.2. Early Termination Visits

If the subject decides to withdraw from the study after randomization, the subject will be asked to complete all follow-up activities that would have been performed at the next scheduled follow-up visit.

Table 2: Schedule of study procedures

Study Phase	Screening & Enrollment	Intervention	Follow-Up: 30 & 60 minutes	Follow-Up: 7 days	Follow-Up: 30 days	Follow-Up: 56 days	Follow-Up: 90 days	Follow-Up: 180 days
Study Days	1	1 (Retreatment Day 2)	1 (Retreatment Day 2)	Final Intervention + 7	Final Intervention + 30	Final Intervention + 56	Final Intervention + 90	Final Intervention + 180
Surveillance Test Review	X							
Medical Record Review	X			X	X	X	X	X
Review Inclusion/Exclusion	X							
Informed Consent	X							
Enteral Access Check	X							
Randomization	X							
Dispense PMT to Clinical Site		X						
PMT Receipt Check		X						
PMT Administration		X						
Compliance Check		X						
Vital Signs Review			X	X				
Symptom Review			X	X	X	X	X	X
Laboratory Review				X	X	X	X	X
CRF3 / Outcomes Check				X	X	X	X	X
Adverse Event Check		X	X	X	X	X	X	X
Immune Phenotypic Analysis on Otherwise Discarded Whole Blood				X				

7. Study Evaluations and Measurements

7.1. *Medical Record Review*

The medical record will be reviewed prior to enrollment, in order to assess eligibility, as outlined above. The medical record will be reviewed at 7-day, 30-day, 56-day, 90-day, and 180-day follow-ups to help ascertain primary and secondary outcomes, as well as adverse events (Sections 3.2 and 9.1.3). HIPAA authorization will be obtained with informed consent.

7.2. *Physical Examination*

Physical examination will include only of vital sign measurements, as below.

7.3. *Vital Signs*

Vital signs will be checked by study team personnel during the 60 minute observation period after product administration. Parameters for notifying the clinical care team of abnormalities are outlined in the study intervention phase section above. Vital signs will be checked while subjects are either sitting or lying down, as per their preference.

7.4. *Laboratory Evaluations*

No laboratory evaluations will be performed as a part of this study. Laboratory values will be collected from review of the subject's electronic medical record, in order to ascertain outcome data and adverse events, as described above.

7.5. *Pregnancy Testing*

Urine pregnancy testing using an FDA-cleared test will be performed as a part of this study.

7.6. *Other Evaluations, Measures*

Subjects who are discharged from the hospital prior to 7 days following their last FMT will be provided with a diary and thermometer to keep track of their temperature (once a day), stool frequency, and any emesis. This diary will be reviewed with subjects at their 7-day follow-up visit.

For the exploratory aim, immune phenotypic analysis using flow cytometry may be performed on a subset of subjects using whole blood collected for clinical purposes, which would otherwise be discarded. Blood will be collected from residual material available in EDTA ("purple top") vacutainer tubes already collected in the clinical laboratory.

7.7. *Efficacy Evaluations*

The primary outcome (time to resolution of R-CDI symptoms) will be assessed at 8 weeks (56 days) following the intervention. The criteria will be assessed via patient interview and electronic medical record review as per Section 3.2.1.

7.8. *Genetic Testing (only if applicable)*

No human genetic testing will be performed. For the exploratory aim, stool microbiome analysis will be performed on stool samples obtained as described in [Section 7.6](#). These stool samples would otherwise be discarded. This will involve sequencing of microbial nucleic acids. This will not involve human DNA sequencing and thus does not comprise genetic testing. Likewise, phenotyping of immune response via flow cytometry may be performed on a subset of subjects, using whole blood collected for clinical purposes that would otherwise be discarded. This will not involve human DNA sequencing and or genetic testing.

7.9. *Safety Evaluations*

7.9.1. Deviations and Exceptions

Exception (Prospective action):

An **exception** is defined as a one-time, intentional action or process that departs from the approved study protocol, intended for one occurrence. If the action disrupts the study progress, such that the study design or outcomes may be compromised, or the action compromises the safety and/or welfare of study subjects, advance documented approval from the Regulatory Sponsor and local regulatory review committees, per institutional guidelines, is required. Approval from the Regulatory Sponsor must be received prior to submission to the local regulatory review committees.

Deviation (Retrospective action):

A **deviation** is defined as a one-time, unintentional action or process that departs from the approved study protocol, involving one incident and identified retrospectively. If the deviation disrupts study progress, such that the study design or outcomes may be compromised, or the deviation compromises the safety and/or welfare of study subjects, the deviation must be reported to the Regulatory Sponsor within 2 days of PI knowledge and to local regulatory review committees per institutional guidelines.

Report the following information on the Sponsor's exception/Deviation form:

- Protocol number
- Subject number
- Description of the exception or deviation
- Impact on subject safety
- Impact on data integrity

Deviations that are assessed by the PI to not disrupt the study progress, such as not affecting the study design or outcome, or compromising the safety and/or welfare of study subjects, should be documented in site records and contain documentation of the PI's assessment.

7.9.2. Safety Parameters

Safety will be monitored in several ways:

- 30- and 60-minute observations with vital sign checks after investigational product administration.

- Follow-up at 7 days, 30 days, 90 days, and 180 days as outlined in the schedule of study procedures ([Table 1](#)).
- Examination of safety-related secondary outcomes, including: bacteremia, mortality, hospital admission, colectomy or diverting ileostomy.

8. Statistical Plan

8.1. Primary Endpoint

The primary endpoint will be proportion of subjects with clinical resolution of diarrhea without recurrence in subjects with R-CDI at 8 weeks (56 days) following FMT. To address the potential for misclassification of subjects who are only NAAT-positive for *C. difficile* (McDonald 2018), the primary analysis will be stratified based on the most recent positive CDI test (NAAT versus EIA) prior to enrollment.

8.2. Secondary Endpoints

Secondary endpoints are detailed in [Section 3.2.2](#). Secondary endpoints will include all-cause mortality (30- and 60-days following last FMT), colectomy or diverting ileostomy within 30 days after last FMT, cumulative days of hospitalization from enrollment until 30 days after FMT, cumulative days in intensive care unit from enrollment until 30 days after last FMT, bacteremia from enrollment until 30 days after last FMT, hospital admission within 60 days of intervention.

8.3. Sample Size and Power Determination

The primary analysis will be stratified based on the most recent positive CDI test (NAAT versus EIA) prior to enrollment. Given the anticipated enrollment of 300 subjects (150 per intervention group), a conservative estimate that 10% of subjects will be lost to follow-up (i.e., minimum subject number 90% of total), and the expectation that the ratio of EIA-positive/NAAT-positive subjects will be 1:2, the expected sample size will be 90 for EIA and 180 for NAAT ($150*0.9=135$ per arm, with a 45:90 ratio for EIA/NAAT). The low-dose cure rate is anticipated to be about 50% in the NAAT group and 70% in the EIA group. Based on these assumptions, the detectable difference between the cure rates for the low and high dose groups for 80% power and varying type I error rates, based on a Chi-square test (two-sided), are provided below.

Stratified Population	Number of subjects (subjects per arm)	Type 1 Error	Power	Detectable difference in proportions compared to 50%
EIA	90 (45)	0.05	0.8	0.7725
EIA	90 (45)	0.1	0.8	0.7458
EIA	90 (45)	0.2	0.8	0.7133
NAAT	180 (90)	0.05	0.8	0.7003
NAAT	180 (90)	0.1	0.8	0.6793
NAAT	180 (90)	0.2	0.8	0.6543

For phase II studies it is typical to accept a type 1 error of greater than 0.05 (Schoenfeld 1980; Khan 2012). For this phase II study, we will accept a difference between intervention groups that meets a type I error threshold of 0.2. Therefore, we will have 80% power to detect a difference of 0.2133 (50% to 71.33%) in the EIA group, and a difference of 15.43% (50% to 65.43%) in the NAAT group. The power calculations were performed using PASS 16 (Power Analysis and Sample Size Software (2018). NCSS, LLC. Kaysville, Utah, USA, ncss.com/software/pass/).

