8.4.2. Efficacy Analysis

An intention to treat analysis will be performed for the primary outcome of clinical resolution of diarrhea without recurrence in subjects with R-CDI at 8 weeks following FMT. A logistic regression model will be used to compare the two study groups (single-dose versus double-dose) to detect superiority of a dose. A p-value (one-sided) of <0.2 will be considered significant. As above, the primary analysis will be stratified based on the most recent positive CDI test (NAAT versus EIA) prior to enrollment. Per protocol analysis will also be performed, based on received (rather than randomized) treatment.

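### Section 8.3 assumes 70% single-dose cure in EIA-positive subjects, but the EIA detectable effects are computed from 50%

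*Combined protocol and SAP*

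**What the plan says.** Section 8.3 sets out the planning inputs: 300 subjects, 10% loss to follow-up and a 1:2 ratio of EIA-positive to NAAT-positive subjects. That leaves 45 EIA and 90 NAAT subjects per arm. It then gives the control rates: "The low-dose cure rate is anticipated to be about 50% in the NAAT group and 70% in the EIA group". The next sentence ties the table to those inputs: "Based on these assumptions, the detectable difference between the cure rates for the low and high dose groups for 80% power". The test is described as "based on a Chi-square test (two-sided").

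The results column is headed "Detectable difference in proportions compared to 50"%, with no distinction between strata. The EIA entries are 0.7725, 0.7458 and 0.7133 for type I error 0.05, 0.1 and 0.2. The NAAT entries are 0.7003, 0.6793 and 0.6543. Section 8.3 adopts the 0.2 level ("we will accept a difference between intervention groups that meets a type I error threshold of 0.2") and concludes: "we will have 80% power to detect a difference of 0.2133 (50% to 71.33%) in the EIA group".

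Section 8.4.2 states the significance rule differently: "A p-value (one-sided) of <0.2 will be considered significant".

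**The concern.** The EIA control rate is 70% in the assumptions and 50% in the calculation, and nothing in section 8.3 reconciles the two. The section does not call 50% a cautious choice for this stratum, although it does call its loss-to-follow-up assumption conservative.

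The EIA stratum is part of the primary analysis, which is stratified by test type (sections 8.1, 8.3 and 8.4.2). Anyone judging whether the EIA target is realistic has only the printed 71.33% to go on. That is 1.33 points above the cure rate already expected from a single dose. What needs to be judged is whether double dosing could plausibly reach a rate in the high eighties.

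A corrected figure also needs a definite alpha. Section 8.3 uses 0.2 two-sided and section 8.4.2 uses 0.2 one-sided, and the answer differs by about 3 points.

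**Working it through.** **Inputs (section 8.3).** n = 45 per arm (EIA) and 90 per arm (NAAT); power 0.80; two-sided alpha 0.05, 0.1 or 0.2; single-dose rate p1 = 0.50 (NAAT) and 0.70 (EIA). The double-dose rate p2 is solved for.

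**Formulas.** Let d = p2 − p1, SE1 = √{[p1(1−p1) + p2(1−p2)]/n}, and z the normal critical value (1.2816 for two-sided 0.2).

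- Unpooled z test, both tails: power = Φ(d/SE1 − z) + Φ(−d/SE1 − z).
- Pooled chi-square: power = Φ[(d − z·SE0)/SE1], with SE0 = √[2p̄(1−p̄)/n] and p̄ = (p1+p2)/2.

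**Step 1: reproduce the plan's table.** With p1 = 0.50 in every row, the unpooled version returns all six printed entries:

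| n per arm | alpha 0.05 | alpha 0.1 | alpha 0.2 |
|---|---|---|---|
| 45 (EIA) | 0.7725 | 0.7458 | 0.7133 |
| 90 (NAAT) | 0.7003 | 0.6793 | 0.6543 |

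For EIA at 0.2: SE1 = √[(0.2500 + 0.2045)/45] = 0.1005; d/SE1 = 0.2133/0.1005 = 2.122; Φ(2.122 − 1.282) = 0.800. The EIA rows therefore come from 50%. The pooled version gives 0.7798/0.7508/0.7163 for EIA, so it is not the method behind the table.

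**Step 2: EIA from the stated 70%, two-sided.**

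| Method | alpha 0.05 | alpha 0.1 | alpha 0.2 |
|---|---|---|---|
| Unpooled z | 0.9218 | 0.9024 | 0.8781 |
| Pooled chi-square | 0.9270 | 0.9061 | 0.8804 |

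Unpooled at 0.2: SE1 = √[(0.2100 + 0.1070)/45] = 0.0839; d/SE1 = 0.1781/0.0839 = 2.122; power 0.800. Exact enumeration of the pooled test at two-sided 0.2 gives power 0.771 at 87%, 0.805 at 87.8% and 0.813 at 88%.

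**Step 3: compare with what is printed (two-sided 0.2).**

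- Detectable difference: 17.8 points (unpooled) or 18.0 (pooled), against 21.33. It is smaller by 3.5 or 3.3 points.
- Double-dose rate required: 87.8–88.0%, against 71.33%. It is higher by 16.5 to 16.7 points.
- Power for a 21.33-point gain from 70% (to 91.33%): 0.916 unpooled, 0.908 pooled, 0.921 exact.
- Power for 70% against 71.33%: about 0.20–0.21 counting both tails, which is essentially the alpha of 0.2.

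**Step 4: sensitivity.** The 70% is given as approximate. At two-sided 0.2 (unpooled), a 65% base requires 84.0% (19.0 points) and a 75% base requires 91.3% (16.3 points).

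**Step 5: the one-sided rule of section 8.4.2.** With z = 0.8416 (one-sided 0.2), EIA from 70% requires 84.63% unpooled or 84.73% pooled, a gain of 14.6–14.7 points. NAAT from 50% requires 62.35% or 62.40%, about 12.4 points, against the printed 65.43%.

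**The case against.** The strongest reply is that the 50% base is in plain view. The column heading names it and the conclusion prints both ends of the comparison, so nobody need read 71.33% as a target starting from 70%. Each entry is correct for its labelled base. Section 8.3 states its conclusion as a difference, and on that scale 50% is cautious: if 70% is right, the stratum can detect about 18 points, less than the 21.33 claimed. Enrolment of 300 is an input to the calculation and no interim analysis is planned, so no design decision rests on the figure. Setting 88% against 71.33% also compares rates reached from different bases. Finally, the one-sided versus two-sided conflict is a separate matter.

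Much of this stands. The concern does not show underpowering in absolute points, and the 17-point gap in rates should be read beside the 18 versus 21.33 comparison. But visible labels do not remove the contradiction, because the text still says the table rests on assumptions that include 70% for EIA.

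Nor does the caution carry over to the odds-ratio scale of the planned logistic regression. Moving from 50% to 71.33% is an odds ratio of 0.7133/0.2867 = 2.49. Moving from 70% to 87.8% is (0.878/0.122)/(0.70/0.30) = 3.08. The alpha conflict is a distinct defect, but it decides which corrected EIA figure applies, so it cannot be left out.

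**Conclusion.** The concern holds. The EIA detectable effect in section 8.3 does not follow from the 70% single-dose rate the same section assumes. At 45 per arm, 80% power and two-sided 0.2, the consistent statement is 70% versus about 88%, a gain of about 18 points. The plan gives 50% versus 71.33%, a gain of 21.33 points. In absolute points the error overstates the detectable difference by about 3.5 points; in terms of the rate to be reached, the printed value is about 17 points too low. If the one-sided rule of section 8.4.2 governs, the EIA figure is about 84.7%.

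These results rest on the plan's own stratum sizes and on 70% being the intended EIA rate; across 65–75% the required rate runs from 84.0% to 91.3% at two-sided 0.2. The NAAT rows are consistent with their stated base. This should be fixed, but it does not threaten the design.

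**What to change.** Preferred: recompute the three EIA rows from 70% and name the method. At two-sided alpha 0.05, 0.1 and 0.2 the entries become 0.922, 0.902 and 0.878 by the unpooled z test that reproduces the present table, or 0.927, 0.906 and 0.880 by the pooled chi-square. Restate the EIA conclusion as 70% versus about 88%, a difference of about 18 points, at two-sided 0.2.

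Alternative: keep the 50% rows and state that 50% is a deliberate EIA planning rate below the anticipated 70%, conservative in absolute points. This documents the choice but still does not give the effect detectable at the expected rate.

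In either case, relabel the column as the detectable double-dose cure rate, since it lists rates and not differences, and show the comparator for each stratum. State one alpha and its sidedness, and make sections 8.3 and 8.4.2 agree. If the one-sided 0.2 rule governs, the recomputed EIA figure is about 84.7% (14.7 points) and the NAAT figure about 62.4% (12.4 points).

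The cost is a restatement of section 8.3, plus an edit to the significance rule in section 8.4.2 if the two-sided level is the one kept. Sample size, allocation and endpoint are unchanged, and the analysis remains a logistic regression.

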8.4. Statistical Methods

8.4.1. Baseline Data

Baseline and demographic characteristics, as well as vital signs, laboratory values, and radiologic study results, will be summarized by standard descriptive statistics (including mean and standard deviation for continuous variables such as age and standard percentages for categorical variables such as gender). Collected variables will include but not be limited to: body mass index (BMI), comorbid medical conditions, use of immunosuppressive medications, use of proton pump inhibitor (PPI) or H2 antagonist medications, use of concurrent non-CDI directed antibiotics, hospital length of stay and level of care. Time between CDI diagnosis and intervention will also be assessed.

8.4.2. Efficacy Analysis

An intention to treat analysis will be performed for the primary outcome of clinical resolution of diarrhea without recurrence in subjects with R-CDI at 8 weeks following FMT. A logistic regression model will be used to compare the two study groups (single-dose versus double-dose) to detect superiority of a dose. A p-value (one-sided) of <0.2 will be considered significant. As above, the primary analysis will be stratified based on the most recent positive CDI test (NAAT versus EIA) prior to enrollment. Per protocol analysis will also be performed, based on received (rather than randomized) treatment.

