1.1. Background and Relevant Literature

As recently as 2015, the Centers for Disease Control and Prevention (CDC) identified *Clostridium difficile* infection (CDI) as an “urgent” threat associated with upwards of 500,000 infections in the United States each year and resulting in over 15,000 deaths. CDI is characterized by a clinical syndrome that typically includes loose, frequent bowel movements and abdominal pain, which occur as a result of toxin production by colonic *C. difficile*. CDI occurs in patients colonized with toxigenic *C. difficile* and in patients who have newly acquired *C. difficile*. Estimates of the relative contributions of persistent colonization and new acquisition to incident CDI vary. In both cases, the pathogenesis of CDI involves depletion of non-*C. difficile* colonic microbiota, altered bile acid metabolism, germination of (resident or recently ingested) *C. difficile* spores, expansion of a population of vegetative *C. difficile*, toxin production, and colonic inflammation. Key challenges

associated with CDI include its recurrence after appropriate antibiotic treatment (R-CDI), and its progression to a more severe disease state with systemic signs of inflammation or even sepsis. The latter, termed severe or severe-complicated/fulminant CDI (S/SC/F-CDI), often requires extended hospitalizations, may require colectomy, and is associated with high rates of mortality (Kelly BJ 2018). At present, antibiotic treatment is the recommended therapy for early R-CDI, and antibiotic treatment followed by FMT is the recommended therapy for later R-CDI. Antibiotics are the recommended therapy for S/SC/F-CDI (McDonald 2018).

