4.1. Inclusion Criteria

1. Second or greater episode of CDI (first or greater recurrence) within 12 months, with symptoms including bowel movement altered in frequency or consistency from baseline.
2. Stool positive for *C. difficile* toxin by EIA or toxin gene by NAAT within 60 days of enrollment.
3. At least one additional prior positive stool test for *C. difficile* within the prior 12 months (EIA or NAAT as above).
4. Age \geq 18 years.
5. Minimum of 72 hours of receipt of standard-of-care (vancomycin or fidaxomicin) antibiotic treatment for R-CDI prior to intervention.

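### Beyond the NAAT/EIA stratification, the primary logistic model prespecifies no baseline covariate; adding three that are collected or ascertained at entry would be a modest, almost free gain in efficiency

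*Combined protocol and SAP*

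**What the plan says.** Section 8.4.2 gives the primary comparison: "A logistic regression model will be used to compare the two study groups (single-dose versus double-dose) to detect superiority of a dose". It adds that "the primary analysis will be stratified based on the most recent positive CDI test (NAAT versus EIA) prior to enrollment", and sets the criterion: "A p-value (one-sided) of <0.2 will be considered significant". Section 8.1 gives the reason for the stratification: "To address the potential for misclassification of subjects who are only NAAT-positive for" *C. difficile*. Section 8.3 treats test type as prognostic: "The low-dose cure rate is anticipated to be about 50% in the NAAT group and 70% in the EIA group".

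No other covariate is named for the primary model. Section 8.4.1 lists further variables for descriptive summary, among them "use of concurrent non-CDI directed antibiotics, hospital length of stay and level of care". Recurrence number is not named in that list, although the list is expressly open-ended. It enters through inclusion criterion 1 in 4.1: "Second or greater episode of CDI (first or greater recurrence) within 12 months". Section 3.1.2 allows treatment of inpatients and outpatients. Section 3.1.5 stratifies randomization by upper versus lower delivery only.

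**The concern.** The trial population is mixed. It combines first with later recurrences and inpatients with outpatients, and subjects may be on other antibiotics. Section 1.1 notes that guidelines separate early from later disease: "antibiotic treatment is the recommended therapy for early R-CDI, and antibiotic treatment followed by FMT is the recommended therapy for later R-CDI". Under 3.2.1 a subject fails on death, on further anti-CDI antibiotics (other than prophylaxis) or on a repeat FMT, so it is plausible that these three factors bear on the outcome.

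Neither the randomization nor the primary model accounts for them. If they do predict cure, adjustment would sharpen the dose comparison and protect against chance imbalance. The trial is open label (5.6), so covariates chosen after outcomes are known would be hard to defend. What is at stake is some power, not validity.

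**Working it through.** **1. The plan's own figure.** Section 8.3 gives 80% power at type I error 0.2, two-sided, for 50% versus 65.43% with 90 per arm (NAAT). With unpooled variance the SE is √[(0.5×0.5 + 0.6543×0.3457)/90] = 0.0727, so z = 0.1543/0.0727 = 2.12. Power is Φ(2.12 − 1.282) = 0.80. For EIA (50% versus 71.33%, 45 per arm) z is also 2.12 and power 0.80. The table reproduces.

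**2. Inputs for the gain.**
- From 8.3: 270 evaluable subjects, NAAT to EIA 2:1, single-dose cure 50% and 70%.
- Assumed, because the documents give nothing: prevalence of first recurrence 40%, concurrent antibiotics 25%, inpatient 40%; independent factors; a shift in cure of 0, 10 or 20 points for each.

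**3. Approximate gain by hand.** Outcome variance left after NAAT/EIA: V = (2/3)(0.5×0.5) + (1/3)(0.7×0.3) = 0.2367. Variance explained by the covariates: S = Σ q(1−q)d², where q is prevalence, d is the shift, and q(1−q) = 0.24, 0.1875 and 0.24. Relative efficiency: E = 1/(1 − S/V).

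| Shift in points (recurrence / antibiotics / inpatient) | S | S/V | E | Equivalent extra subjects, 270×(E−1) |
|---|---|---|---|---|
| 0/0/0 | 0 | 0 | 1.00 | 0 |
| 10/10/10 | 0.0067 | 0.028 | 1.03 | 8 |
| 20/20/10 | 0.0195 | 0.082 | 1.09 | 24 |
| 20/20/20 | 0.0267 | 0.113 | 1.13 | 34 |

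Simulated logistic models with NAAT/EIA in both the smaller and the larger model gave the same efficiencies: about 1.00, 1.03, 1.09 and 1.13.

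**4. Power at one-sided 0.2 (critical value 0.842).** Take an assumed 8-point dose effect, for which simulated power without the covariates was about 67%. Then z = 0.842 + 0.440 = 1.282. Multiplying by √E gives 1.300, 1.338 and 1.361 for the last three rows, and power of 67.7%, 69.0% and 69.8%. The gain is 0 to about 3 points.

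**5. At the plan's own effect.** A second simulation used the NAAT effect of 8.3 (50% to 65.43%) and three covariates, each with assumed prevalence 30% and a common odds ratio (4,000 trials per row). From a 50% cure rate, odds ratios 0.67, 0.5 and 0.33 mean shifts of about 10, 17 and 25 points (0.67/1.67 = 0.40; 0.5/1.5 = 0.33; 0.33/1.33 = 0.25).

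| Odds ratio | Pooled power, without → with | NAAT alone | EIA alone | SD of standardized difference | Variance ratio |
|---|---|---|---|---|---|
| 1.0 | 94.9 → 94.8% | 90.1 → 89.5% | 67.2 → 67.0% | 0.0573 → 0.0579 | 0.98 |
| 0.67 | 94.9 → 95.1% | 90.6 → 90.8% | 66.5 → 66.4% | 0.0570 → 0.0567 | 1.01 |
| 0.5 | 95.3 → 95.9% | 89.6 → 91.0% | 67.3 → 68.8% | 0.0557 → 0.0542 | 1.06 |
| 0.33 | 95.5 → 96.7% | 89.6 → 92.7% | 66.6 → 70.4% | 0.0563 → 0.0517 | 1.19 |

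The last column is (SD without / SD with)². Pooled power is already about 95%, so it has little room to rise. The last row lies beyond the 20-point range used in step 3.

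**6. Error rate.** With no dose effect, the adjusted model rejected in 20.7% of 3,000 simulated trials at nominal 20% and in 10.4% at nominal 10%. The Monte Carlo SE at 20% is √(0.2×0.8/3,000) = 0.7 points, so no material inflation is seen.

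**The case against.** A reader might infer that the primary model ignores patient-level prognosis altogether. It does not. Test type is a patient-level baseline factor, 8.3 assumes a 20-point difference in cure between its levels, and the analysis is stratified on it.

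A reader might also infer that the plan throws precision away. The documents do not support that either. No passage says that recurrence number, level of care or concurrent antibiotics predicts cure after FMT. Section 1.1 reports that guidelines recommend different therapy for early and later recurrence, which is not a statement about cure rates. Every prevalence and effect above is assumed, and a 20-point shift per factor equals the largest prognostic difference the plan itself assumes.

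Further points on the other side stand:
- Section 8.4.1 fixes no time point for level of care or concurrent antibiotics, and recurrence number is not a named data item.
- The documents do not settle whether the strata give one pooled test or two. If EIA is modelled alone, 70% cure in 90 subjects leaves about 27 failures (90×0.3), or fewer if the second dose helps. That is thin support for dose plus three more terms.
- The 8-point effect is not the plan's. At the plan's NAAT effect the pooled change is only −0.1 to +1.2 points.
- Route, the randomization stratum, is not named in the model either. That is a separate gap.

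Hospital length of stay might be read as a post-randomization variable used as a covariate. The plan only summarizes it descriptively, so no planned analysis needs correcting.

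One further argument carries less weight: that adjustment raises the SE of the treatment log-odds ratio (pooled, from about 0.263 without the covariates to 0.291 with them at odds ratio 0.33). The coefficient rises as well (0.644 to 0.769), and on the difference scale the spread falls.

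**Conclusion.** The point holds as an optional improvement. NAAT/EIA is the only baseline factor prespecified in the primary analysis, and three plausible covariates can be had at almost no cost. The analysis as written is valid.

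With assumed shifts of 0 to 20 points per factor and the assumed prevalences, the gain equals about 0% to 13% more subjects. At one-sided 0.2 that is about 0 to 3 points of power for an assumed 8-point dose effect, and less in a pooled model at the effect used for sizing. If the factors are not prognostic, the loss is negligible (at most 0.6 points in the simulations above). The size rests wholly on assumed prognostic strength; that no such covariate is prespecified does not.

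**What to change.** In 8.4.2, keep NAAT/EIA and prespecify three further covariates in the primary model:
- concurrent non-CDI antibiotic use at randomization (yes or no);
- inpatient versus outpatient status at randomization;
- recurrence number (first versus second or later).

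Add recurrence number to the baseline form; it is already ascertained when inclusion criterion 1 is checked. Report the dose effect as a standardized difference in cure proportions: average the model's predicted cure under each dose over all analyzed subjects, then subtract. Do this within each stratum as well if the strata are tested separately, so that the result is on the scale of 8.3.

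The cost is SAP wording, three model terms and one baseline field. The extra terms matter mainly if the 90 EIA subjects are modelled on their own. The change should be made before outcome data are examined.
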